4.0 Methodology

4.1 Study Design

A prospective cohort study of 1200 pregnant women (600 HIV positive and 600 HIV negative). **Figure 1** below is the study flow diagram.

Viral load re-testing with be done for all Unsuppressed HIV load every 3 months

Figure 1: Study Flow Diagram

Key

*Pregnancy outcome include spontaneous abortions, birth defects, multiple births, low birth weights preterm infants, birth with prolonged hospitalization, birth requiring neonatal intensive care, maternal, perinatal and infant deaths.

**Coinfections include HBV, HCV, CMV and intestinal parasites

***NCD, non-communicable diseases (hypertensive disorders, malnutrition, diabetes)

**** For acute HIV infections ONLY

*****Adverse feotal outcomes include preterm birth (<37 weeks of gestation) low Apgar score<7, low birth weight, Fetal macrosomia, birth weight of more than 4,000 grams, birth defects, stillbirth (death of a fetus weighing \geq 500g or \geq 22 weeks gestation if weight is unavailable), early neonatal death (death between 0-6 days of life), neonatal death (death within the first 28 days of life), neonatal jaundice, infant death, intensive care unit admission, hospital admissions including documented local clinic treatments

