	different comorbidities in isolation or combinations among mothers and infants.
	uniterent comorbiances in isolation of comornations among motiers and infants.
	-
	4. To correlate maternal plasma viral load, soluble biomarkers immune activation profiles and diseases
	4. To correlate maternal plasma viral load, soluble biomarkers immune activation profiles and diseases progression and duration of HAART treatment among HIV+ mothers
	 To correlate maternal plasma viral load, soluble biomarkers immune activation profiles and diseases progression and duration of HAART treatment among HIV+ mothers To determine any association of different HAART regimens and pregnancy outcome, infant growth and
Primary	 To correlate maternal plasma viral load, soluble biomarkers immune activation profiles and diseases progression and duration of HAART treatment among HIV+ mothers To determine any association of different HAART regimens and pregnancy outcome, infant growth and immune/neuro-development among HIV+ mothers
Primary end points	 To correlate maternal plasma viral load, soluble biomarkers immune activation profiles and diseases progression and duration of HAART treatment among HIV+ mothers To determine any association of different HAART regimens and pregnancy outcome, infant growth and immune/neuro-development among HIV+ mothers Prevalence, trends and incidence of comorbidities among HIV+ and HIV- mothers
•	 To correlate maternal plasma viral load, soluble biomarkers immune activation profiles and diseases progression and duration of HAART treatment among HIV+ mothers To determine any association of different HAART regimens and pregnancy outcome, infant growth and immune/neuro-development among HIV+ mothers Prevalence, trends and incidence of comorbidities among HIV+ and HIV- mothers Pregnancy outcomes for HIV-/+ mothers with different comorbidities with or without different HAART
•	 To correlate maternal plasma viral load, soluble biomarkers immune activation profiles and diseases progression and duration of HAART treatment among HIV+ mothers To determine any association of different HAART regimens and pregnancy outcome, infant growth and immune/neuro-development among HIV+ mothers Prevalence, trends and incidence of comorbidities among HIV+ and HIV- mothers Pregnancy outcomes for HIV-/+ mothers with different comorbidities with or without different HAART regimens

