Components leading to healthy pregnancy outcome include healthy pre-pregnancy weight, appropriate weight gain, physical activity during pregnancy, consumption of a wide variety of foods, appropriate vitamin and mineral supplementation, avoidance of alcohol, other harmful substances and safe food handling ¹⁶⁶. Nutritional assessment needs to encompass changes in anthropometric, biochemical and clinical indicators throughout pregnancy 166. Due to some challenges associated with these measurements plasma insulin growth factor-1 (IGF-1) offers a potentially; simple but accurate single measurement of nutritional status alongside with total protein, creatinine, urea nitrogen, albumin, complement components C3/C4 and α -1 anti-trypsin¹⁶⁷. Maternal anthropometry, haemoglobin concentration, serum iron, total iron binding capacity (TIBC) and serum albumin were assessed and the incidence of preterm labour was significantly higher in mothers with severe anaemia¹⁶⁸. Anaemia is to be defined as Hb below 11.0 g dl⁻¹ and severe anaemia as Hb below 7.0g dl⁻¹ (WHO, 1991).Poor maternal bodyweight and low body mass index (BMI) have been associated with low birth weight in HIV-infected women ^{169;170}. Birth weight is largely determined by maternal factors other than hyperglycaemia, with the most significant influences being gestational age at delivery, maternal prepregnancy body mass index (BMI), maternal height, and pregnancy weight gain, the presence of hypertension, cigarette smoking and alcohol use. Anthropometric assessments of mid-upper arm circumference (MUAC) have also been shown to be an efficient, cost-effective screening tool for low birth weight in both HIV-infected and uninfected women ¹⁷¹. Low MUAC has been associated with poor maternal health outcomes, including anaemia.¹⁷². Taking multivitamins during pregnancy may be an inexpensive and effective strategy to improve the health of the mother and baby. MUAC measurements of <11.0 cm among children has been associated significantly elevated risk of mortality¹⁷³. An improvement in prenatal mean haemoglobin concentration linearly increased birth weight ¹⁷⁴. On the other hand maternal obesity is associated with increased risk of gestational hypertension, preeclampsia, gestational diabetes and feotal macrosomia, high birth weight (>4,000 grams).Accumulating evidence links vitamin D deficiency with abnormal glucose metabolism and

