4.10.18 Sample Size Determination

Pocock's formula was used to determine sample size (n) required:

- $n = \frac{p_1(1-p_1)+p_2(1-p_2)(Z_{\alpha}-Z_{\beta})^2}{(p_1-p_2)^2}$
- Where p_1 and p_2 are proportion of success in population 1 and 2
- Z_{α} and Z_{β} are values of standard normal distribution
- α = Significance level
- $\beta = Power$

3% incidence rate has been assumed to factor in for the a high risk of vertical transmission in the breastfeeding period for the few anticipated acute HIV infection²³⁴.With the advent of cell phones the % loss to follow up may not be that bad and cannot be similar for the first and second year. Factored in the worst case scenario of a 15% and 20% loss to follow-up during the first and second year respectively, a minimum sample size required computed using **STATA** is 1200 (600 HIV+ and 600 HIV-) mothers. Assuming a 15% and 20% loss to follow up in the first and second year of the study respectively, should leave us with at least the 417 infants. The sample size has power to predict diseases outcomes of HEU children which must culminate in their improved management. The sample size has not factored in sample sizes of sub-studies linked to it in the **Appendices' Section 6.2**. Should there be sub-studies, they should fit within this parent protocol. These aim to address all the research gaps highlight throughout the literature review.

	a) HIV Chronic Infection		b) HIV Acute Infection	c) HIV Negative	Outcomes
Comorbidities	Treatment experienced Immune	Treatment naive Profiles for dif	ferent comorbidities c	ombinations	Prevalence and incidence of comorbidities, comorbidities trends relating comorbidities to
HBV HCV CMV					immunological profiles, pregnancy outcomes, vertical transmission of infections, patterns and
Anaemia Diabetes Nutritional Status					transmission linkages, infant/child growth and neurodevelopment
Hypertensive disorders					

Table 5: Pictorial Depiction of the Stratification

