4.10.22 Data analysis

The data were collected and analyzed using SPSS (version17.0, Chicago, IL). Viral load values were log₁₀ transformed. The Student's t-test was used to compare means. Regression analysis was used to investigate the associations Tests of statistical significance included the 95% confidence interval of unadjusted relative risks, two-sided p values based on Chi-square and Fisher's exact tests. Sequences were assembled using the Vector NTI Advance 10 program. Alignment was attained using Gene Doc, BioEdit, and Clustal X2 sequence alignment programs including manual editing to ensure that deletions or insertions did not alter the reading frame.

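### Birth weight is named as an outcome only in categories; weight in grams should be reported alongside low birth weight and macrosomia

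*Protocol*

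**What the plan says.** The Primary end points row of the Protocol Summary includes "Pregnancy outcomes for HIV-/+ mothers with different comorbidities with or without different HAART" regimens. The Protocol Summary's objective on regimens is "To determine any association of different HAART regimens and pregnancy outcome" and infant development among HIV-positive mothers.

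The content of pregnancy outcome is set out in the key to Figure 1 (section 4.1), in two lists. The pregnancy outcome list has "low birth weights preterm infants" among events such as abortion, birth defects and death. The adverse fetal outcome list has "low Apgar score<7, low birth weight, Fetal macrosomia, birth weight of more than 4,000 grams". Macrosomia is therefore in the second list only. Low birth weight is in both, without a gram cut-off. Weight in grams is not named as an outcome in either list, in the objectives (section 3.1) or in the research outcomes (section 4.10.24).

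For categorical data, section 4.10.21 names the chi-squared test, and section 4.10.22 names "the 95% confidence interval of unadjusted relative risks, two-sided p values based on Chi-square" and Fisher's exact tests. For continuous variables the same sections name analysis of variance, rank-sum tests, the t-test and regression, without saying which variables they apply to.

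**The concern.** Birth weight has to be measured before it can be classified, so the grams will exist. Reduced to low birth weight yes or no, each infant contributes only the side of the cut on which its weight falls. When an exposure moves the whole distribution by a modest amount, most of the evidence lies in weights that stay on the same side of the cut. The main hypotheses (section 2.1) are stated as no difference between HIV-positive and HIV-negative women, so the ability to detect a modest difference matters for this end point. The regimen comparison is tighter still, because it uses only the HIV-positive half of the cohort.

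**Working it through.** **Inputs.** From the protocol: "1200 (600 HIV+ and 600 HIV-) mothers", and two-sided p values (section 4.10.22). The protocol gives no birth-weight mean, SD, low-weight cut-off or target difference. The sample size section has no values for the two proportions, the significance level or the power, and its only rate, 3%, concerns HIV. There is thus no protocol figure on birth weight to reproduce. Assumed: normal weights, low birth weight (LBW) below 2,500 g, mean/SD of 3,000/500 g or 3,100/450 g, a uniform deficit of 60 to 100 g, and two-sided 5%.

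**Formulas.**
- Grams: power = Φ(d / (SD·√(2/n)) − 1.96).
- LBW: p = Φ((2500 − mean)/SD) and q = Φ((2500 − mean + d)/SD). Power = Φ((|q−p|·√n − 1.96·√(2·p̄(1−p̄))) / √(p(1−p)+q(1−q))), where p̄ = (p+q)/2.

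**Worked case: mean 3,000, SD 500, d = 80, n = 600.**
- Grams: SE = 500·√(2/600) = 28.87; 80/28.87 = 2.77; Φ(2.77 − 1.96) = 0.79.
- LBW: p = Φ(−1.00) = 0.159, q = Φ(−0.84) = 0.200, power 0.47.

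| Mean / SD | Deficit | LBW risks | Power, LBW | Power, grams |
|---|---|---|---|---|
| 3,000 / 500 | 60 g | 15.9% v 18.9% | 0.29 | 0.55 |
| 3,000 / 500 | 80 g | 15.9% v 20.0% | 0.47 | 0.79 |
| 3,000 / 500 | 100 g | 15.9% v 21.2% | 0.66 | 0.93 |
| 3,100 / 450 | 60 g | 9.1% v 11.5% | 0.27 | 0.64 |
| 3,100 / 450 | 80 g | 9.1% v 12.4% | 0.45 | 0.87 |
| 3,100 / 450 | 100 g | 9.1% v 13.3% | 0.64 | 0.97 |

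Crossing the two means with the two SDs at 80 g widens LBW power to 0.41-0.52; grams stay at 0.79-0.87. At mean 3,000 and SD 500, 80% power for 100 g needs 393 per group in grams and 836 as LBW.

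**Information kept by the cut.** φ(z)²/(p(1−p)) is 0.44 for p = 0.159 and 0.33 for p = 0.091.

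**Pooling both tails.** If LBW and more than 4,000 g were combined into one yes/no outcome, power for 100 g would be 0.48 (3,000/500) or 0.39 (3,100/450), because a downward shift fills one tail and empties the other.

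**Regimen comparison.** At most 600 mothers. Two equal regimen groups would be 300 v 300, so SE = 500·√(2/300) = 40.8. For 80 g, power is 0.50 in grams; the same formulas give 0.265 as LBW. For 3,100/450 they are 0.59 and 0.25.

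**Effect only through preterm birth (all inputs assumed).** Term weights 3,100-3,150 g (SD 400-430), preterm 2,200-2,400 g (SD 400-450), preterm share rising from 8-10% to 13-16%, 600 per group. Example: term 3,100/400, preterm 2,200/400, share 10% to 16%. The mean falls by 0.06 × 900 = 54 g, LBW goes from 13.7% to 18.0%, and power is 0.46 in grams and 0.52 as LBW. Across these settings power is about 0.24-0.49 in grams and 0.24-0.57 as LBW, with LBW equal or slightly ahead. Adding a general shift of 40 g restores an advantage of roughly 12-22 points to grams.

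**The case against.** The strongest reply is that the plan does not confine birth weight to categories. Both lists are introduced as inclusive, they are lists of clinical events in a figure key, and sections 4.10.21 and 4.10.22 provide methods for continuous variables. The choice of scale could also be made in an analysis plan not at hand. This stands in part. A reader might infer that analysis in grams is excluded, and the documents do not say so. Still, the protocol fixes what the end point contains, and weight in grams is not in it.

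The power figures also rest on a uniform shift. The background (sections 1.0 and 1.2.4) points to preterm delivery, and under that pathway alone the gain disappears. Opposing effects, such as large infants with gestational diabetes and growth restriction with hypertension, could cancel in a mean. This stands, and it is why grams belong beside the categories and not in their place.

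Two background statements might be taken as further support, but neither carries much. "An improvement in prenatal mean haemoglobin concentration linearly increased birth weight" (section 1.6) is one cited result on haemoglobin and says nothing of HIV or HAART. The remark in section 1.2.4 on missing regional standards concerns birth weight by gestational age, so it does not undermine a fixed gram category.

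**Conclusion.** The point holds in a limited form. Birth weight is named within a primary end point only in categories, and the continuous methods are not attached to it. If an exposure shifts the whole distribution, analysis as low birth weight alone costs 32 to 42 percentage points of power for an 80 g deficit (0.79 − 0.47 and 0.87 − 0.45) at 600 per group. If it acts only through more preterm births, there is no loss. All birth-weight inputs are assumptions, so the size is illustrative.

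Three stronger readings are not supported. One is that 1,200 weights serve every contrast: 1,200 is a ceiling, reduced by fetal loss and missed deliveries, and the regimen comparison has at most 600 mothers. Another is that grams must be the lead analysis, which is a preference. The third is that null results will be taken as confirming the hypotheses of no difference; no section says how they will be read.

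**What to change.** In the Figure 1 key, name birth weight in grams as a continuous outcome in addition to low birth weight and macrosomia, and state the gram cut-off used for low birth weight. In section 4.10.22, add that birth weight will be reported as a mean difference with 95% CI from linear regression on HIV status, comorbidity or, among HIV-positive mothers, regimen. Keep low birth weight and macrosomia as separate proportions with CIs, not pooled into one yes/no outcome.

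The change costs a few sentences and one further analysis. Weight must already be measured to be classified, and regression is already a named method. The small downside is that a mean difference is less directly clinical than a proportion, which is why both are shown.

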4.2 Study Sites

City of Harare poly-clinics, that offer maternal and child health services.

4.3 Study Participants

ANC mothers registering at the ante-natal clinicsat 28-36 weeks gestation will be enrolled. Upon delivery, babies will be automatically recruited into the study and be followed up as mother-baby pairs for two years.

4.4 Inclusion Criteria

- Pregnant woman 18 years of age and above at 28-36 weeks gestation. The date of the last menstrual period (LMP) will be used to estimate gestational age.
- Planning to deliver at the study sites
- Able to give informed consent
 - Willing to be followed together with her baby from delivery up to two years
 - Willing to provide the required specimens

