2.1 Main Hypotheses

- There is no difference in the prevalence and incidence of co-morbidities (anaemia, malnutrition, hypertension, diabetes, HCV, HBV, CMV) and immune profile of HIV+ and HIV- pregnant women and the impact of these comorbidities on pregnancy outcome and infant growth and development within 24 months post-delivery is similar.
- 2. There is no difference in biomarkers of inflammation and immune activation profiles among HIV+ and HIV- mothers with different comorbidities and their HEI, HUU HEU infants.

3.0 Project Goals:

- 1. The main goal of this study is to characterise co-morbidities, immunogenetics of pregnant women and their infants in Harare and ascertain their roles in disease acquisition and transmission
- 2. Contribute to the knowledge base on the role of HIV and human immunogenetics on acquisition and disease progression and co-infections in children.

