4.8 Mothers' Procedures

• A questionnaire will be administered at enrolment from which information regarding their sociodemographics, sexual behaviour and reproductive health issues including obstetrical records will be obtained. Antiretroviral use and regimen will be recorded for all the HIV+ mothers. Assessment of nutritional status/BMI will be done using standard anthropometric indices. A physical examination will be done at every visit by the study clinician. Mothers will be enrolled at 28-36 weeks gestation and followed up at delivery, 10 days and 6, 10, 14, 24, 36, 48, 72 and 96 weeks postpartum thus totaling 11 visits during the study period. Data can still be collected in cases of missed visits provided the participant turns up within the seven day window period of the scheduled visits. The participant may be asked to discontinue if she consecutively fails to turn up for at least two successive scheduled study visits without any reason(s).

Biological specimens blood, cord blood, amniotic fluid, breast milk urine and stool will be collected at different visit with the respective quantities and purposes as shown in the **Table** 1 below.

	Total Volume of Specimen Required						
Visit	HIV Status	Blood* (mL)	Stool** (grams)	Breast Milk* (mL)	Urine *** (mL)	Amniotic Fluid (mL)	Cord Blood (mL)
1	HIV+	30	20	-	100	50	
In Pregnancy	HIV-	25	20		100	50	
2 Delivery	HIV+	10	20		100	50	50
	HIV-	5	20		100	50	50
3 7 -10 days pp	HIV+	-	If delivery visit is	10	100		
	HIV-	-	missed some of the samples are collected.	10	100		
4 6 Weeks/1½Months pp	HIV+	20	20	10	100		
	HIV-	10	20	10	100	50	
5 10 Weeks /2½ Months	HIV+	20	20	10	100		
рр	HIV-	10	20	10	100		
6 14 Weeks, 3½Months	HIV+	20	20	10	100		
рр	HIV-	10	20	10	100		
7 24 Weeks/6 Months pp	HIV+	20	20	10	100		
	HIV-	10	20	10	100		
8 36 Weeks/9 Months pp	HIV+	20	20	10	100		
	HIV-	10	20	10	100		
9 48 Weeks/1 year	HIV+	20	20	10	100		
pp	HIV-	10	20	10	100		
10 72 Weeks /1 ^{1/2} years	HIV+	20	20	10	100		
	HIV-	10	20	10	100		
11 96 Weeks/2 years	HIV+	20	20	10	100		
	HIV-	10	20	10	100		

Table 1: Types and total Volumes of Maternal Specimen Required

*Generally blood samples, amniotic fluid cord blood and breast milk will be tested for trend in immune profiles and coinfections.

Stool samples will be tested for intestinal parasites * Urine

urinalysis

Procedure	Specimen	1	2	3	4	5	6	7	8	9	10	11

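### Last menstrual period, taken at 28-36 weeks, is the only dating source the protocol names, so preterm birth will be misclassified and its risk ratio probably weakened; better dating data can be captured only if the enrolment form asks for them

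*Protocol*

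**What the plan says.** **Dating rule.** Section 4.4 (Inclusion Criteria) states "The date of the last menstrual period (LMP) will be used to estimate gestational age". The same bullet sets the entry window: "Pregnant woman 18 years of age and above at 28-36 weeks gestation". The protocol names no scan, fundal height, neonatal maturity score or item on certainty of the date as a dating source. It does not say separately how gestational age at delivery is obtained.

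**Outcome.** The key to Figure 1 (section 4.1) lists "Adverse feotal outcomes include preterm birth (<37 weeks of gestation) low Apgar score<7, low birth weight" among adverse outcomes, and its list of pregnancy outcomes also includes preterm infants: "Pregnancy outcome include spontaneous abortions, birth defects, multiple births, low birth weights preterm infants". The Protocol Summary makes pregnancy outcome by HIV status, comorbidity and drug regimen a primary end point. It gives as a primary objective "To determine any association of different HAART regimens and pregnancy outcome". Section 2.1 takes as a null hypothesis that "the impact of these comorbidities on pregnancy outcome and infant growth and development within 24 months post-delivery is similar".

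**Other information collected.** Under section 4.8, the enrolment questionnaire covers items such that "sexual behaviour and reproductive health issues including obstetrical records will be obtained". No dating use of those records is stated.

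**Analysis.** Section 4.10.22 plans unadjusted relative risks with 95% confidence intervals and two-sided tests.

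**The concern.** The date is asked for six months or more after the event, and the answer feeds a hard cut-point. Most births fall within a few weeks above 37 weeks, so even a modest dating error moves many term births across the line. True preterm births are fewer and move the other way. The observed preterm group then contains a large share of term births, and a real contrast by HIV status or regimen is diluted.

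Timing makes this more than an analysis detail. Certainty of the date, and any earlier estimate in the woman's records, have to be captured at enrolment. A later analysis plan cannot reliably recover them if the form did not ask.

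**Working it through.** The protocol gives no preterm rate, dating error or power for preterm birth, so there is no stated figure to reproduce. Everything below except the 37-week cut and the group size is an assumption.

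**Inputs.** Cut at 37 weeks (section 4.1); 600 women per HIV group (section 4.10.18); two-sided 5% level, taken from the 95% intervals in section 4.10.22. Assumed: true preterm rates 10% and 15%; true gestation normal with SD 1.8 weeks; error in the date-based gestation normal with mean b and SD e.

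**Formula.** The group mean is m = 37 - z(p) x 1.8, which gives 39.31 weeks for 10% and 38.87 weeks for 15%. The observed preterm rate is Φ[(37 - m - b) / √(1.8² + e²)].

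Example with e = 2, b = 0: √(3.24 + 4) = 2.691. Then Φ(-2.307/2.691) = 19.6% and Φ(-1.866/2.691) = 24.4%, a ratio of 1.25.

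**Equal random error in both groups (b = 0):**

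| Error SD (weeks) | Observed rates | Risk ratio | Risk difference (points) | Truly preterm among observed preterm, 10% group | Power, 600 per group |
|---|---|---|---|---|---|
| 0 | 10.0% v 15.0% | 1.50 | 5.0 | 100% | 75% |
| 1 | 13.1% v 18.2% | 1.39 | 5.1 | 57% | 68% |
| 2 | 19.6% v 24.4% | 1.25 | 4.8 | 33% | 53% |
| 3 | 25.5% v 29.7% | 1.17 | 4.2 | 24% | 37% |

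Power = Φ{[|p1 - p0|√n - 1.96√(2p̄(1 - p̄))] / √[p0(1 - p0) + p1(1 - p1)]}.

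**A different shape for true gestation.** This uses a mixture of a term group (mean 39.3, SD 1.2) and an early group (mean 35, SD 2.2), weighted to the same true rates. At error SD 1, 2 and 3 weeks, the risk ratios are 1.34, 1.17 and 1.10. The risk differences are 4.7, 3.7 and 2.9 points (true 5.1), and power is 60%, 33% and 20%. The ratio shrinks under both shapes, but the risk difference shrinks clearly only under this one.

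**Direction.** Suppose the date overstates gestation on average, with SD 1. In the normal model, b = +0.5 week gives 8.6% v 12.5% (ratio 1.45) and b = +1 week gives 5.4% v 8.2% (ratio about 1.51). In the mixture, b = +1 gives 7.6% v 11.7% (ratio 1.54). Preterm birth is then under-counted and the ratio is roughly kept. Power at b = +1 still falls, to 48% and 67%.

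**Unequal error with no true difference.** In the mixture with 12% truly preterm in both groups, error SD 3 weeks in one group against 2 in the other gives a false ratio of 1.27. Error SD 1 against 2 gives 0.67. A half-week bias in one group gives 1.25 or 0.79, depending on its sign.

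**What better dating could recover.** In the mixture, suppose the error SD falls from 2 weeks to 1 in 25%, 50% or 100% of women. The ratio rises from 1.17 to 1.20, 1.24 or 1.34, and power rises from 33% to 39%, 44% or 59%.

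Both models ignore that women must still be pregnant at enrolment, so they indicate size only.

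**The case against.** - **The dating sentence belongs to eligibility, and records are not barred from use.** This is fair as far as it goes: that no other source will be used is read from silence. But the sentence is worded generally and no other rule exists for delivery. If another is intended, the protocol needs to state it.
- **Inflation is not certain.** This stands. A reader might infer that the preterm rate must be too high, but the documents do not settle the direction of error, and a date that overstates gestation lowers the rate.
- **Shrinkage depends on the scale.** This stands in part. In the normal model the risk difference hardly moves at SD 1 or 2. The loss is in the ratio and in power.
- **Nothing shows that error differs by HIV status.** This stands. A reader might infer it from section 1.11, which ties unplanned pregnancy and late antenatal care to vertical transmission. That section does not say either is commoner in HIV-positive women, and both groups share the same entry window. Distortion specific to drug regimen has no support beyond the general dilution.
- **Form fields and sensitivity analyses belong in other documents.** This stands for the analyses. It does not stand for the data: the protocol fixes the dating method, and what is not captured at enrolment may be lost.
- **Dating by scan wherever one exists could itself bias the comparison.** This stands. Scans may be unevenly available, and a late scan can make a growth-restricted fetus look younger. Excluding births on implausible weight would select on birth weight, itself a listed outcome. The fix avoids both.

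**Conclusion.** The concern holds in limited form. As written, the protocol dates pregnancies from a recalled last menstrual period and gives no separate rule at delivery, so preterm birth will be misclassified. With equal random error of SD 1 to 3 weeks and true rates of 10% and 15%, the risk ratio of 1.50 falls to 1.39-1.17, or 1.34-1.10 under the more skewed gestation model. Power at 600 per group falls from about 75% to 68%-37%, or 60%-20%.

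These sizes rest wholly on assumed rates and error SDs. The documents support neither a definite direction of bias nor a claim that a contrast by HIV status or regimen would be spurious. Unequal error could create or hide a contrast, but that is a possibility to check. This is a cheap improvement worth making, not a flaw that invalidates the study.

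**What to change.** 1. At enrolment, record how certain the woman is of the date. From the obstetric records already obtained, copy any earlier dating information and the gestation at which it was made.
2. State in advance which source defines gestational age at delivery. Let a scan override the recalled date only if it was done early enough in pregnancy to be more accurate, with that limit written down. Apply the same rule to both HIV groups.
3. Report the availability of each dating source by HIV status, so that any imbalance is visible.
4. Repeat the preterm analysis in women with a certain date or corroborating early dating. Do not exclude births on birth weight; at most, use an implausible weight to query the date.

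**Cost.** A few form fields and one extra analysis, with no new scans or visits. The protocol gives no cost figure. The restricted analysis has fewer women. The gain depends on how many records hold usable early dating; since women are enrolled on registering at 28-36 weeks (section 4.3), that number may be small. Certainty of the date can be recorded for every woman regardless.
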